11.1 Definitions

11.1.1 Unanticipated Problems Involving Risk to Subjects or Others (UPIRTSO)

Any unanticipated problem or adverse event that meets the following three criteria:

- Serious: Serious problems or events that results in significant harm, (which may be physical, psychological, financial, social, economic, or legal) or increased risk for the subject or others (including individuals who are not research subjects). These include: (1) death; (2) life threatening adverse experience; (3) hospitalization - inpatient, new, or prolonged; (4) disability/incapacity - persistent or significant; (5) birth defect/anomaly; (6) breach of confidentiality and (7) other problems, events, or new information (i.e. publications, DSMB reports, interim findings, product labeling change) that in the opinion of the local investigator may adversely affect the rights, safety, or welfare of the subjects or others, or substantially compromise the research data, **AND**
- Unanticipated: (i.e. unexpected) problems or events are those that are not already described as potential risks in the protocol, consent document, or not part of an underlying disease. A problem or event is "unanticipated" when it was unforeseeable at the time of its occurrence. A problem or event is "unanticipated" when it occurs at an increased frequency or at an increased severity than expected, **AND**
- Related: A problem or event is "related" if it is possibly related to the research procedures.

11.1.2 Adverse Event

An untoward or undesirable experience associated with the use of a medical product (i.e. drug, device, biologic) in a patient or research subject.

11.1.3 Serious Adverse Event

Adverse events are classified as serious or non-serious. Serious problems/events can be well defined and include;

- death
- life threatening adverse experience
- hospitalization
- inpatient, new, or prolonged; disability/incapacity
- persistent or significant disability or incapacity
- birth defect/anomaly

and/or per protocol may be problems/events that in the opinion of the sponsor-investigator may have adversely affected the rights, safety, or welfare of the subjects or others, or substantially compromised the research data.

All adverse events that do not meet any of the criteria for serious, should be regarded as **non-serious adverse events**.

11.1.4 Adverse Event Reporting Period

For this study, the follow-up period is defined as up to 10 minutes after arrival to PACU or TOF ratio is > 0.9 (whichever occurs first).

11.1.5 Preexisting Condition

A preexisting condition is one that is present at the start of the study. A preexisting condition should be recorded as an adverse event if the frequency, intensity, or the character of the condition worsens during the study period.

11.1.6 Post-study Adverse Event

All unresolved adverse events should be followed by the sponsor-investigator until the events are resolved, the subject is lost to follow-up, or the adverse event is otherwise explained. At the last scheduled visit, the sponsor-investigator should instruct each subject to report, to the sponsor-investigator, any subsequent event(s) that the subject, or the subject's personal physician, believes might reasonably be related to participation in this study.

11.1.7 Hospitalization, Prolonged Hospitalization or Surgery

Any adverse event that results in hospitalization or prolonged hospitalization should be documented and reported as a serious adverse event unless specifically instructed otherwise in this protocol. Any condition responsible for surgery should be documented as an adverse event if the condition meets the criteria for an adverse event.

Neither the condition, hospitalization, prolonged hospitalization, nor surgery are reported as an adverse event in the following circumstances:

- Hospitalization or prolonged hospitalization for therapy of the target disease of the study, unless it is a worsening or increase in frequency of hospital admissions as judged by the clinical investigator.

11.2 Recording of Adverse Events

At each contact with the subject, the study team must seek information on adverse events by specific questioning and, as appropriate, by examination. Information on all adverse events should be recorded immediately in the source document, and also in the appropriate adverse event section of the electronic case report form (CRF). All clearly related signs, symptoms, and abnormal diagnostic, laboratory or procedure results should be recorded in the source document.

All adverse events occurring during the study period must be recorded. The clinical course of each event should be followed until resolution, stabilization, or until it has been ultimately determined that the study treatment or participation is not the probable cause. Serious adverse events that are still ongoing at the end of the study period must be followed up, to determine the final outcome. Any serious adverse event that occurs during the Adverse Event Reporting

Period and is considered to be at least possibly related to the study treatment or study participation should be recorded and reported immediately.

11.3 Reporting of Serious Adverse Events and Unanticipated Problems

When an adverse event has been identified, the study team will take appropriated action necessary to protect the study participant and then complete the Study Adverse Event Worksheet and log. The sponsor-investigator will evaluate the event and determine the necessary follow-up and reporting required.

11.3.1 Sponsor-Investigator reporting: notifying the Mayo IRB

The sponsor-investigator will report to the Mayo IRB any UPIRTSOs and Non-UPIRTSOs according to the Mayo IRB Policy and Procedures. Each participating site will report SAEs to their respective IRB or Ethics Committee with copy of submission and review provided to the leading site. Should there be any SAEs at any of the participating sites; the study team at that site will notify the primary site (Mayo Clinic in Florida) within 24 hours of learning of the event.

Any serious adverse event (SAE) which the Principal Investigator has determined to be a UPIRTSO will be reported to the Mayo IRB as soon as possible but no later than 5 working days after the investigator first learns of the problem/event.

The following information will be collected on the adverse event worksheet (and entered in the research database):

- Study ID
- Disease
- The date the adverse event occurred
- Description of the adverse event
- Relationship of the adverse event to the research device*
- Determination if the adverse event was expected
- The severity of the adverse event (severity scale described below**)
- If any intervention was necessary
- Resolution (was the incident resolved spontaneously, or after discontinuing treatment)
- Date of Resolution

The sponsor-investigator will review all adverse event reports to determine if specific reports need to be made to the IRB. The sponsor-investigator will sign and date the adverse event report when it is reviewed. For this protocol, only directly related SAEs/UPIRTSOs will be reported to the IRB.

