*** Relationship Index**

The relationship of an AE to the Investigational Device is a clinical decision by the sponsor-investigator (PI) based on all available information at the time of the completion of the eCRF and is graded as follows:

1. Not related: a reaction for which sufficient information exists to indicate that the etiology is unrelated to the use and proper application of study device.
2. Unlikely: a clinical event, including laboratory test abnormality, with a temporal relationship to use of the study device which makes a causal relationship improbable and in which use of other devices, chemicals, or underlying disease provide plausible explanations.
3. Possible: a clinical event, including laboratory test abnormality, with a reasonable time sequence to use of the study device but which could also be explained by concurrent disease or use of other devices or chemicals.
4. Probable: a clinical event including laboratory test abnormality, with a reasonable time sequence to use of the study device, unlikely to be attributed to concurrent disease or use of other devices or chemicals.
5. Definite: a reaction that follows a reasonable temporal sequence from the use of the study device.

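### Section 11.3.1 limits IRB reports to 'directly related' events, which contradicts its own opening rule and the 'possibly related' threshold in 11.1.1

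*Combined protocol and SAP*

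**What the plan says.** Four places in section 11 bear on which events reach the IRB.

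- **11.1.1 (UPIRTSO definition).** An event must be serious, unanticipated and related, all three together. The third criterion is met "if it is possibly related to the research procedures".
- **11.2 (Recording of Adverse Events).** A serious adverse event in the reporting period that is "considered to be at least possibly related to the study treatment or study participation should be recorded and reported immediately". No recipient is named.
- **11.3.1 (notifying the Mayo IRB).** It opens: "The sponsor-investigator will report to the Mayo IRB any UPIRTSOs and Non-UPIRTSOs according to the Mayo IRB Policy and Procedures". For an SAE that the Principal Investigator has determined to be a UPIRTSO, the report is due "no later than 5 working days after the investigator first learns of the problem/event". The sponsor-investigator reviews every adverse event report to decide whether the IRB must be told. The section then ends: "For this protocol, only directly related SAEs/UPIRTSOs will be reported to the IRB".
- **Relationship Index (following 11.3.1).** Relation to the study device is graded in five steps: not related, unlikely, possible, probable, definite. The *Possible* grade describes an event "with a reasonable time sequence to use of the study device but which could also be explained by concurrent disease" or by other devices or chemicals.

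**The concern.** The closing sentence of 11.3.1 is worded as a study-specific limit, and the word *only* makes it exclusive. It sets a relatedness condition that appears nowhere else in the protocol and looks stricter than the one in 11.1.1. A UPIRTSO is by definition at least possibly related, so applying a *directly related* filter to UPIRTSOs can only remove some of them.

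What is at stake is whether the IRB hears of events that the protocol itself defines as unanticipated problems involving risk. This is more than a missing detail: it is a stated rule that, followed as written, gives the opposite answer to the rule at the head of the same section. Nor can the sponsor-investigator apply it consistently, because the worksheet collects a five-step relationship grade and nothing says which steps count as *directly related*.

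**Working it through.** No arithmetic applies. The check is to take one event through each rule.

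**Test event:** serious, unanticipated, and judged possibly related to the research procedures.

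1. *11.1.1:* serious, yes; unanticipated, yes; related, yes, because possible relation is enough. The event is a UPIRTSO.
2. *11.3.1, opening sentence:* it covers any UPIRTSO. The event goes to the IRB.
3. *11.3.1, deadline:* once the Principal Investigator has determined that the SAE is a UPIRTSO, it goes to the IRB within 5 working days. No further relatedness condition is attached.
4. *11.3.1, closing sentence:* the event goes to the IRB only if it is *directly* related. An event judged merely possible does not meet that on the plain meaning of the words. The event does not go to the IRB.

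Steps 2 and 3 conflict with step 4. The conflict needs only 11.1.1 and 11.3.1.

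**Can the Relationship Index settle what *directly related* means?** No. None of its five grades carries that name, and no sentence maps the grades to a reporting duty. What relatedness refers to also shifts between sections: research procedures in 11.1.1, study treatment or participation in 11.2, and the study device in the worksheet and Index.

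**Do other readings of the closing sentence remove the conflict?**

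- *It qualifies both SAEs and UPIRTSOs and narrows them.* The conflict is as shown above.
- *It qualifies SAEs only.* All UPIRTSOs are still reported, so the test event reaches the IRB. But a possibly related SAE that is not a UPIRTSO is then excluded by the closing sentence, while the opening sentence includes Non-UPIRTSOs, subject to IRB policy.
- *It means the same as related in 11.1.1.* The test event reaches the IRB, but the qualifier then does no work for UPIRTSOs, and the text does not say that this is what is meant.

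The documents do not state which of the three is intended.

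**The case against.** The best case on the other side has several parts.

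- **The sentence is ambiguous.** Relatedness is already part of the UPIRTSO definition, so it is arguable that *directly related* was meant to qualify SAEs alone. This stands as a possible reading. It narrows the conflict but does not remove it, and the text does not select that reading.
- **It is not known which sentence the team would follow.** A reader might infer that the study-specific sentence would govern in practice. The documents do not support that: the 5-working-day rule is equally specific and mandatory, and nothing ranks one above the other. What can be said is that two statements disagree.
- **Section 11.2 may not concern the IRB.** A reader might take its immediate-reporting rule as an IRB duty that 11.3.1 breaks. It names no recipient and could mean a report to the sponsor-investigator. It points the same way as 11.1.1 but cannot carry the finding.
- **Relationship grades alone make nothing reportable.** A reader might conclude that every event graded Possible or Probable is wrongly excluded. That goes too far: 11.1.1 also requires the event to be serious and unanticipated, and the Index grades relation to the device rather than to research procedures.
- **IRB policy is not in the documents.** The opening sentence of 11.3.1 defers to it, so how far Non-UPIRTSOs must be reported cannot be judged here. This stands. The conflict over UPIRTSOs does not depend on it.
- **Practical weight is low.** The study is observational, uses an FDA-approved monitor, and under 11.1.4 has an adverse event reporting period ending no later than 10 minutes after PACU arrival. This limits how often the rule would matter, but the inconsistency remains.

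The wording of the *Definite* grade, which asks only for a reasonable temporal sequence, is a separate drafting matter. Changing it would not decide which events go to the IRB.

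**Conclusion.** The inconsistency is real. Section 11.3.1 contradicts itself and the relatedness threshold in 11.1.1, through an undefined term that does not appear on the Relationship Index. Taken literally, its last sentence would withhold from the IRB a serious, unanticipated, possibly related event.

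It would be wrong to infer that such an event goes unrecorded. Under 11.2, 11.3 and 11.3.1 it is still entered in the source document and CRF, put on the worksheet and log, and reviewed and signed by the sponsor-investigator. The gap is in notification to the IRB.

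Its size cannot be put in numbers, because the documents give no expected event rate; it is bounded by the serious, unanticipated events arising in 50 participants. Sample size and primary analysis are unaffected. The conclusion on UPIRTSOs assumes that *directly related* applies to UPIRTSOs as well as SAEs and is stricter than *possibly related*. If it applies to SAEs alone, the narrower conflict over Non-UPIRTSOs remains. The correction should be made because it protects participants and costs very little.

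**What to change.** Reconcile 11.3.1 with 11.1.1 in one of two ways:

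- delete the last sentence of 11.3.1, leaving the opening rule and the 5-working-day deadline to govern; or
- keep the sentence but replace *directly related* with the 11.1.1 definition (possibly related). In that case also say how Non-UPIRTSOs are handled, since the opening sentence includes them and *only* would otherwise still exclude some.

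Either way, state which Relationship Index grades satisfy the 11.1.1 criterion and whether relatedness is judged against the device, the research procedures or study participation. In 11.2, name the recipient of the immediate report.

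The cost is a protocol wording change and at most a few more IRB reports in a 50-patient study. No data collection or analysis changes.

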*** Relationship Index**

The relationship of an AE to the Investigational Device is a clinical decision by the sponsor-investigator (PI) based on all available information at the time of the completion of the eCRF and is graded as follows:

1. Not related: a reaction for which sufficient information exists to indicate that the etiology is unrelated to the use and proper application of study device.
2. Unlikely: a clinical event, including laboratory test abnormality, with a temporal relationship to use of the study device which makes a causal relationship improbable and in which use of other devices, chemicals, or underlying disease provide plausible explanations.
3. Possible: a clinical event, including laboratory test abnormality, with a reasonable time sequence to use of the study device but which could also be explained by concurrent disease or use of other devices or chemicals.
4. Probable: a clinical event including laboratory test abnormality, with a reasonable time sequence to use of the study device, unlikely to be attributed to concurrent disease or use of other devices or chemicals.
5. Definite: a reaction that follows a reasonable temporal sequence from the use of the study device.

**** Severity Scale**

The maximum intensity of an AE during a day should be graded according to the definitions below and recorded in details as indicated on the CRF. If the intensity of an AE changes over a number of days, then separate entries should be made having distinct onset dates.

1. Mild: AEs are usually transient, requiring no special treatment, and do not interfere with patient's daily activities.
2. Moderate: AEs typically introduce a low level of inconvenience or concern to the patient and may interfere with daily activities, but are usually ameliorated by simple therapeutic measures.
3. Severe: AEs interrupt a patient's usual daily activity and traditionally require systemic drug therapy or other treatment.

11.4 Medical Monitoring

It is the responsibility of the Principal Investigator to oversee the safety of the study at his/her site. This safety monitoring will include careful assessment and appropriate reporting of adverse events as noted above, as well as the construction and implementation of a site data and safety-monitoring plan (see section 10 “Study Monitoring, Auditing, and Inspecting”). Medical monitoring will include a regular assessment of the number and type of serious adverse events.

12 Data Handling and Record Keeping

12.1 Confidentiality

Information about study subjects will be kept confidential and managed according to the requirements of the Health Insurance Portability and Accountability Act of 1996 (HIPAA). Those regulations require a signed subject authorization informing the subject of the following:

- What protected health information (PHI) will be collected from subjects in this study
- Who will have access to that information and why
- Who will use or disclose that information
- The rights of a research subject to revoke their authorization for use of their PHI.

In the event that a subject revokes authorization to collect or use PHI, the investigator, by regulation, retains the ability to use all information collected prior to the revocation of subject authorization. For subjects that have revoked authorization to collect or use PHI, attempts should be made to obtain permission to collect at least vital status (long term survival status that the subject is alive) at the end of their scheduled study period.

12.2 Source Documents

Source data is all information, original records of clinical findings, observations, or other activities in a clinical trial necessary for the reconstruction and evaluation of the trial. Source data are contained in source documents. Examples of these original documents and data records include: hospital records and any forms completed specifically for this study.

12.3 Case Report Forms

All data necessary for this study will be obtained from EHR or at the time devices are being used and recorded on the electronic Case Report Forms (CRFs) created in REDCap. All missing data will be explained.

12.4 Data Management

Study data to be collected and managed using EHR and study-generated source documents and transcribed into electronic CRFs in REDCap, electronic data capture software, hosted by CTSA at Mayo Clinic. REDCap (Research Electronic Data Capture) is a secure, web-based application designed to support data capture for research studies, providing 1) an intuitive interface for validated data entry; 2) audit trails for tracking data manipulation and export procedures; 3) automated export procedures for seamless data downloads to common statistical packages; and 4) procedures for importing data from external sources.

12.5 Data Processing

All study data will be stored and analyzed at Mayo Clinic in Florida using the REDCap electronic data capture tool.

12.6 Data Security and Confidentiality

All source documents including clinical findings, observations or other activities will be stored in a REDCap database that will be designed by an Investigator. Access to the REDCap database will be limited to the Principal Investigator, Investigators, Study Team members, and Statistician.

12.7 Data Quality Assurance

Once the study is completed the Principal Investigator will randomly select 3 participants and compare the data documented in the EHR with what is entered into the REDCap database. If there is any discrepancy, the Principal Investigator and/or Investigators will cross-reference all 50 patients to ensure accuracy.

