8.1 Description

TetraGraph device is a FDA approved neuromuscular transmission monitor capable of measuring the depth of neuromuscular block in anesthetized patients who received neuromuscular blocking agents. TetraGraph uses EMG to measure the muscle action potentials that are generated in response to electrical neurostimulation via skin (ECG) electrodes.

TetraGraph data is recorded on the monitor's built-in SD card, and all intraoperative data will be recorded and later downloaded for purposes of analysis. The recorded data do not contain PHI, only the date/time of recording, and any additional intraoperative interventions, such as the time of NMBA dose administration, time of antidote administration, time of extubation, etc. These events are flagged in the monitor's integrated SD card recordings.

Cardiac Output will be measured continuously (as per standard of care) through pulmonary artery catheter, which is the passing of a thin tube into the right side of the heart and arteries leading to the lungs. This catheter will be used as part of the standardized management during the surgical procedure.

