9.2 Visit 2 (Treatment – day of surgery)

- Elective surgical procedure as per standard of care
- Anesthetic management will be at the discretion of the attending anesthesiologist as per standard of care practice.
- Prior to induction of anesthesia, Tetragraph electrodes will be placed over the ulnar nerve and the thumb and/or pinky finger to measure the response of adductor digit minimi nerve (location of Tetragraph will be at a discretion of the anesthesiologist).
- Following induction of anesthesia but prior to NMBA administration, baseline values will be recorded after calibration.
- Cardiac output will be measured continuously through the pulmonary artery catheter and the values will be obtained from EHR.
- Near the conclusion of the operation but prior to the reversal of NMBA, a set of measurements will be taken
- After sugammadex administration, measurements will be taken every 20 seconds until consecutive measurements demonstrate a TOFR ≥ 0.9 (adequate recovery)
- Each neurostimulation with the TetraGraph will be conducted simultaneously with one observer.
- Time to recovery following SGX (TOFR ≥ 0.9) will be documented as well as time to extubation.
- Following measurements obtained the device will be removed and the patient will proceed along the standard recovery pathway.

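### Does the primary recovery time need its own check against the TetraGraph SD card, given that section 12.7 compares REDCap only with the EHR?

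*Combined protocol and SAP*

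**What the plan says.** Section 12.7 is the only place where entered data are to be compared with a source: "the Principal Investigator will randomly select 3 participants and compare the data documented in the EHR with what is entered into the REDCap database". Any discrepancy extends the comparison to all 50 participants. No comparator other than the EHR is named.

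For cardiac output, 9.2 states: "Cardiac output will be measured continuously through the pulmonary artery catheter and the values will be obtained from EHR". Section 6.6 also takes from the medical record the time and dose of the reversal agent, the extubation time and, where available, the TOF ratio at extubation.

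Recovery time appears in two kinds of record:

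- **Device record (8.1).** The TetraGraph writes to an SD card, and "all intraoperative data will be recorded and later downloaded for purposes of analysis". On NMBA dose, antidote and extubation times it says: "These events are flagged in the monitor" recordings.
- **Case report form (6.6, 12.3 to 12.5, 18.2).** The study team fills in TOFR on a 20-second grid and a summary recovery time based on two consecutive readings. Under 12.4, data come from the EHR and "study-generated source documents and transcribed into electronic CRFs in REDCap". The same section lists, among REDCap's functions, "procedures for importing data from external sources". Section 12.5 adds: "All study data will be stored and analyzed at Mayo Clinic in Florida using the REDCap electronic data capture tool".

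No passage says which record prevails if the two differ, or which of the two consecutive readings sets the time.

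**The concern.** Time to TOFR ≥ 0.9 is one of the two variables in the primary correlation (6.4, 10.2). A check that looks only at the EHR is not written to find an error in a value held on the form and the SD card. If the form entry is what gets analysed, a misread or mistyped time could pass unnoticed. The escalation to all 50 would not help, because it uses the same comparator.

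At stake would be a correlation pulled towards zero and a less precise slope. The alternative looks cheap: one variable for 50 participants, from files that 8.1 says will be downloaded anyway.

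**Working it through.** **1. What 12.7 can and cannot reach**

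| Item | Source in the plan | Within an EHR–REDCap comparison? |
|---|---|---|
| Cardiac output | EHR (9.2) | Yes |
| Sugammadex time (start of interval) | Medical record (6.6); also form (18.2) and SD-card flag (8.1) | Yes |
| Moment TOFR ≥ 0.9 is reached | Form (18.2) and SD card (8.1) | Not as written |

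The uncovered part is therefore the end of the interval, not the whole variable. It has two records. The form also holds the individual 20-second readings beside the summary time, so a wrong summary can be seen on the same page. A misrecorded reading would show only against the SD card.

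**2. Are the passages on the data source in conflict?** No. Section 8.1 says the download serves the analysis, 12.4 allows external data to be imported into REDCap, and 12.5 places the analysis data there. A download imported into REDCap satisfies all three. The plan names a source and omits a rule of precedence.

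**3. The plan's own power figure.** Inputs from 10.1 and 10.2: r = 0.6, n = 50, two-sided alpha 0.05.

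Power = Φ(atanh(0.6) × √(50 − 3) − 1.96) = Φ(0.6931 × 6.856 − 1.96) = Φ(2.79) = 99.7%.

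This agrees with the stated figure of more than 90%.

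**4. Effect of random error in recovery time.** Let R be the reliability of the recorded time. R is assumed, because the documents give no error rate.

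- Expected correlation: 0.6 × √R.
- Power: Φ(atanh(0.6√R) × √47 − 1.96).
- Slope standard error relative to no error: √((0.64 + 1/R − 1)/0.64), where 0.64 = 1 − 0.6².

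| R | Expected r | Power (formula) | Power (simulation, 200,000 runs) | Slope SE ratio |
|---|---|---|---|---|
| 1.0 | 0.600 | 99.7% | 99.7% | 1.00 |
| 0.9 | 0.569 | 99.3% | 99.4% | 1.08 |
| 0.8 | 0.537 | 98.4% | 98.5% | 1.18 |
| 0.6 | 0.465 | 93.2% | 93.6% | 1.43 |
| 0.5 | 0.424 | 87.4% | 87.9% | 1.60 |

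With n = 50, 90% power corresponds to r = 0.440. Power therefore falls below 90% only when R < (0.440/0.6)² = 0.54. Error variance would then be 1/0.54 − 1 = 0.85 times the true between-patient variance, an error standard deviation of √0.85 = 0.92 times the true one. That is extreme for recording or transcription slips. Random error in the outcome leaves the slope unbiased.

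**5. Which of the two readings counts?** They are 20 seconds apart, so using the second instead of the first adds 20 seconds for every participant. If one convention is applied throughout, the Pearson correlation, the Spearman correlation and the slope on the raw scale do not change; only the intercept moves. After the log transformation that 10.2 allows, the convention has some effect, so it should be fixed once for all participants.

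**6. Would adding the SD card to the 3-patient check help?** Not much. If 5 of the 50 records were wrong (an assumption), the chance that a random 3 include at least one is 1 − C(45,3)/C(50,3) = 1 − 14,190/19,600 = 27.6%. Only a comparison of all 50 would be a real check, and analysts who derive the time from the download have the material for it.

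**The case for a change.** The strongest case for a change is that a primary variable should not depend on analysts choosing well. Section 12.8 resolves queries only once they are raised, 13.1 and 13.2 give access for monitoring and audit, and REDCap's validated entry and audit trails do not compare a value with its source. The monitoring plan mentioned in 11.4 is not in the documents, so it cannot be counted either way. The form gives the sugammadex clock time only in hours and minutes, which is coarse beside a 20-second grid. One added sentence would cost almost nothing.

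Much of this is factually right. Section 12.7 is not written to verify the moment of recovery, and no rule of precedence exists. The hours-and-minutes point matters only if clock times are subtracted; the form's rows already count seconds from sugammadex.

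The step from there to a needed change does not stand. The plan does name the device download as material for analysis, and the risk is small if that is used. No stated rule or figure is shown to give a wrong result. The SD card is also not proven to be the better record throughout, since an event flag can be missing or implausible, so making it govern by rule is a preference.

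**Conclusion.** No change to the plan is called for. This is missing operational detail that analysts would fill sensibly: they download the SD-card files as 8.1 says, take the recovery time from them or check the form against them, and apply one convention for the two consecutive readings. Writing this down would be a harmless clarification, but nothing in the design, sample size or conclusions depends on it.

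Under assumed random error, the expected correlation falls from 0.60 to between 0.57 and 0.46 for reliabilities of 0.9 to 0.6. Power stays at 93% or more, and the slope's standard error grows by 8% to 43% without bias. Only below a reliability of about 0.54 does power drop under the stated 90%.

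These figures assume independent random error in recovery time alone and the planned r = 0.6 with n = 50. Error that tracked cardiac output would bias the slope. The documents give no basis for sizing it and no sign that it is expected.
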